#### **Test Product, Dose and Mode of Administration:**

The dosage regimen of ATG-010 specified as follow: Subjects will be administered as a fixed oral ATG-010 of 60 mg twice weekly (e.g., Monday and Wednesday or Tuesday and Thursday, etc.) on Weeks 1-4 of each 4-week cycle (total of 8 doses per cycle).

Subjects who achieved partial response (obtained the expected best efficacy judged by

investigator) or better response will transition to maintenance dosing until either PD or occurrence of unacceptable toxicity.

The maintenance dose of ATG-010 will be 60 mg orally QW. Subjects whose dose has been reduced such that the total weekly dose is <60 mg will continue that tolerated dose. If a patient experiences a subsequent increase in disease burden, or per the discretion of the Investigator, the dose of ATG-010 can be increased to 60 mg orally twice weekly, after discussion with the Medical Monitor.

If more than one different type of toxicity occurs concurrently, the most severe grade will determine the modification. All subjects who have a treatment delay of more than 28 days due to drug-related adverse events will withdraw from the study treatment. Each dose modification or treatment delay must be documented in the eCRF, including the respective reason.

### **Concomitant Medications:**

To minimize nausea after oral administration of study drug, all subjects must receive 5-hydroxytryptamine (5-HT3) antagonists (eg, ondansetron 8 mg or equivalent), unless contraindicated, starting before the first dose of ATG-010 and continued twice daily to 3 times daily, after which the specific frequency of medication can be determined by the actual symptoms of the patient. Olanzapine is also recommended for the first 8 weeks, after which the dosage can be gradually reduced according to the situation of patient. Alternative antineoplastic may be provided if the patient does not tolerate 5-HT3 antagonists. Other anti-nausea and anti-anorexia drugs may be administered by the investigator per institutional guidelines (National Comprehensive Cancer Network® [NCCN] Antiemetic Clinical Practice Guidelines® and NCCN Palliative Care Clinical Practice Guidelines)

The best supportive care of study permitted includes blood product transfusions, antimicrobials, and growth factors including granulocyte colony-stimulating factors (for neutropenia), erythropoietins (for anemia), and/or platelet-stimulating factors (for thrombocytopenia).

Concurrent therapy with any authorized or ongoing investigative anticancer agents is not allowed. Subjects are not allowed to participate in any other clinical trials during the study.

### **Study Endpoints:**

#### **Primary endpoint**

- ORR by central radiological review: PR + CR

#### **Secondary endpoints**

- ORR evaluated by investigator
- DOR (evaluated by central radiological review), defined as the duration of time from first occurrence of CR or PR until the first date that disease progression is objectively documented
- DCR (evaluated by central radiological review), defined as the proportion of subjects who achieve CR, PR, or SD for a minimum of 4 weeks, following the first dose of study drug (ie, CR+PR+SD)
- OS, defined as the duration of time from the first dose of study drug until death due to any cause
- PFS, defined as the duration of time from the first dose of study drug until progression or death due to any cause

- PFS, ORR, DOR, DCR, and OS in subjects with DH-DLBCL and non-DH- DLBCL; with GCB and non-GCB DLBCL; and with “very good”, “good”, and “poor” R-IPI
- Safety and tolerability

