#### Study Rationale:

ATG-010 (Selinexor) is an orally bioavailable selective inhibitor of nuclear export (SINE) compound that specifically blocks exportin 1 (XPO1). Preclinical studies showed that ATG-010 can lead to the nuclear accumulation and re-activate of tumor suppressor proteins and other growth modulators, promote rapid onset of apoptosis both *in vitro* and *in vivo* of hematological and solid tumor cells; meanwhile it has little effect on normal cells. SADAL is an international, multicenter, open IIb, ongoing study. As of 15 November 2018, the efficacy data (Karyopharm, 2018) for SADAL Study were updated and ORR was 29.6% by central radiology laboratory based on 115 subjects in modified intent-to-treat (mITT) population, including CR 9.6% and PR 20.0%; the median DOR was 9.2 months in all ATG-010 responders

(total 34 subjects; 11 CRs+23 PRs), median DOR in CR subjects was 23 months, and median DOR in PR subjects was 7.8 months. The median OS was 9.1 months in all subjects, 29.7 months for CR/PR subjects, but only 3.2 months for progressive disease/not reached (PD/NR) subjects. These results showed the correlation between tumor responses of DLBCL and clinical efficacy of treatment, the OS observed in ATG-010 non-responders with PD/NR was also consistency with published references.

Based on the encouraging clinical efficacy and safety data obtained by ATG-010 monotherapy in the treatment of subjects with recurrence or refractory DLBCL, FDA granted the rapid channel of ATG-010 monotherapy for recurrence or refractory DLBCL on 07 November 2018, aiming at accelerating the clinical study and marketing approval of ATG-010.

According to the efficacy data obtained by SADAL Study in the population of relapse or refractory DLBCL subjects in the west, the current study plans to verify the clinical efficacy of ATG-010 single drug treatment in subjects with relapse/refractory DLBCL who have received no more than 5 systematic treatment regimens in the past.

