### **Discontinuation Criteria:**

A subject may be discontinued at the discretion of the Investigator for any of the following reasons, the investigator should make the decision after timely communication with the clinical trial monitor in specific cases.

- Disease progression, as assessed by the Investigator and confirmed by the central radiological review, defined according to the revised Lugano criteria for response assessment of lymphoma (Cheson, 2014)
  - For subjects with disease progression on imaging assessment, if disease progression is not clearly unequivocal and/or the patient is clearly deriving clinical benefit, after discussion with the Sponsor Medical Monitor, the Investigator may elect to continue the patient on study and repeat imaging within 4 to 8 weeks for confirmation or negation of PD.
- Disease progression as determined by the Investigator (should be radiographically confirmed whenever possible and must be comprehensively documented by the Investigator)
- Unacceptable adverse event(s) or failure to tolerate the study treatment
- Treatment delay of more than 28 days, except in specific cases approved by the Sponsor
- Any medically appropriate reason or significant protocol violation, in the opinion of the Investigator

The Investigator must remove a patient from study treatment for any of the following reasons:

- Patient decides to discontinue study treatment or withdraws consent
- Pregnancy

Subjects may decide to discontinue study treatment for any reason. Subjects who elect to discontinue study treatment will be asked to continue study participation so that follow-up information on disease progression and survival status may be obtained.

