### **Statistical Summaries:**

The primary endpoint analyses will be conducted after at least one efficacy evaluation following the enrollment of the last patient to the study (including efficacy and safety), and the amended analyses on efficacy and safety will be conducted after the End of Study.

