### ***Efficacy Assessment***

The primary endpoint analyses will be based on ORR data evaluated by central radiological review. The mITT population will be used for analyses of efficacy, which is defined as all subjects who received at least 1 dose of study drug administration.

Analysis of ORR will also be conducted in per-protocol population (PP) and this population will be used for supportive efficacy analysis.

The PP population will consist of the following subjects in the mITT population:

- Compliance of ATG-010 treatment  $\geq 70\%$ ;
- Subjects who have received at least one complete post-baseline tumor evaluation, except for the subjects who died before or withdrew from study;
- Subjects who have no major protocol violations that would compromise the assessment of efficacy.

Data lists of major violations that would compromise the statistical analysis will be determined prior to database lock.

The secondary efficacy endpoints include ORR evaluated by investigator, DOR and DCR evaluated by central radiological review, OS, and PFS, etc, which will be analyzed using the mITT and the per protocol populations. Time-to-event with censored value (DOR, PFS and OS, etc) will be assessed using Kaplan-Meier methods in survival analysis, 95% CIs will be provided for ORR and DCR.

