- 21 Disease assessment (tumor measurement) will be made by PET-CT and Contrast-enhanced CT (Tumor measurement) at screening (within the first 14 days of Cycle 1 Day 1), enhanced CT should include the neck, chest, abdomen, pelvic cavity (including the inguinal/femoral region), if clinically indicated, as well as other anatomical sites. If CT is contraindicated, MRI scan will be performed. PET-CT and contrast-enhanced CT scans will be performed on Cycle 3 Day 1 ( $\pm 1$  week) and then every 8 $\pm 1$  weeks (ie, Day 1 of odd numbered cycles) until disease progression is confirmed by the central radiological review. The PET-CT is allowed at alternating assessment time points (ie, every 16 weeks, or every other scan) if PET-CT cannot be performed for every assessment. If CT scan suggests the possibility of obtaining CR, PET-CT should be performed for confirmation. Results of PET-CT and contrast-enhanced CT scans performed beyond a predetermined time point should be recorded on the eCRF and images of all disease assessment scans performed during the study period will be provided to the central radiological review.
- 22 Disease status will be assessed by the Lugano criteria for response assessment of lymphoma (*Cheson, 2014; Appendix 1*) on Cycle 3 Day 1 ( $\pm 1$  week) and then every 8 weeks  $\pm 1$  week (ie, Day 1 of odd numbered cycles) until disease progression is confirmed by the central radiological review.
- 23 Bone marrow aspirates and/or biopsies will be taken within 1 month prior to first dose (baseline) to assess DLBCL involvement in bone marrow. The bone marrow biopsy will be repeated whenever clinically indicated to confirm CR in only those subjects who had DLBCL known bone marrow involvement prior to dosing.
- 24 To minimize nausea, all subjects should receive 5-HT3 antagonists (8 mg or equivalent) unless contraindicated, starting on Cycle 1 Day 1 before the first dose of ATG-010 and continued 2 to 3 times daily thereafter, as needed. Olanzapine is also recommended for the first 8 weeks, after which the dosage can be gradually reduced according to the situation of patient.
- 25 ATG-010 dosing will occur on Days 1 and 3 of Weeks 1-4 of each 4-week cycle. For doses on non-clinic days, the patient will be provided doses to take home.

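### Duration of response ends only at documented progression, while PFS also ends at death, so DOR is overstated if a responder dies without centrally documented progression

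*Combined protocol and SAP*

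**What the plan says.** Under Secondary endpoints, DOR by central radiological review is "defined as the duration of time from first occurrence of CR or PR until the first date that disease progression is objectively documented". Death is not mentioned. Two bullets later the list gives "PFS, defined as the duration of time from the first dose of study drug until progression or death due to any cause".

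The Efficacy Assessment section puts both under one method: "Time-to-event with censored value (DOR, PFS and OS, etc) will be assessed using Kaplan-Meier methods". It does not say which observations are censored, or when.

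DOR is a listed secondary objective and is also to be reported by double-hit status, cell of origin and R-IPI group. The Study Rationale cites SADAL as the reference ("the median DOR was 9.2 months in all ATG-010 responders") without saying whether death counted as an event there.

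Some provisions limit the problem. Scans continue until central review confirms progression, and "images of all disease assessment scans performed during the study period will be provided to the central radiological review" (Table 1, footnote 21). Subjects who choose to stop treatment "will be asked to continue study participation so that follow-up information on disease progression and survival status may be obtained" (Discontinuation Criteria).

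**The concern.** A responder who dies with no centrally documented progression has a PFS event but no DOR event. The documents do not say that such a responder is censored; that is the consequence of this definition under Kaplan-Meier. Censoring treats the subject as still able to remain in response, which a dead subject is not. Deaths of this kind are possible here. A fatal infection between 8-week scans leaves no progression to document, and the Discontinuation Criteria let a subject stop on investigator-determined progression, for which imaging confirmation is expected only where feasible.

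In a single-arm study there is no control arm in which the same bias could cancel. Any reading of DOR beside SADAL's 9.2 months is like for like only if the two event definitions match, and the documents do not show that they do. DOR and PFS would also follow different event rules in the same responders.

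**Working it through.** **The plan's own figure.** The only design figure is power above 90%. 20.7% of 60 is 12.42, so at least 13 responders are needed; P(X ≥ 13 | n = 60, p = 0.283) = 0.903. This agrees with the plan and does not depend on how DOR is defined. No stated figure does.

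**Direction.** At a death without documented progression, the progression-or-death curve drops and the progression-only curve does not, while both lose one subject from the risk set. With censoring at the death date, the progression-only curve therefore never lies below the other. With censoring at the last scan and ±1-week scan windows, the simulated median was lower in at most 0.2% of runs.

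**Inputs from the documents.** 60 subjects and ORR 28.3% (Determination of Sample Size), so 0.283 × 60 ≈ 17 responders; median DOR 9.2 months and responder OS ("29.7 months for CR/PR subjects") from the Study Rationale; 6 months of enrolment and 12 months of follow-up after the last enrolment (Duration of Study).

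**Assumptions.** Constant hazards; 9.2 months is a progression-or-death median; response at 2 months, so follow-up from response is uniform on 10 to 16 months; a share s of response-ending events are deaths without documented progression.

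**Events by end of study.** λ = ln 2 / 9.2 = 0.0753 per month.
P(event) = 1 − [exp(−10λ) − exp(−16λ)] / (6λ) = 1 − (0.4708 − 0.2996) / 0.4521 = 0.621, and 17 × 0.621 = 10.56 events. With response at 4 months, 9.51.

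**Effect of censoring the deaths.** The hazard becomes λ(1 − s). The median becomes 9.2 / (1 − s), the 12-month rate exp[−12λ(1 − s)], and P(at least one such death) = 1 − (1 − 0.621s)^17.

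| s | Expected deaths | P(at least one) | Reported median (months) | Reported 12-month rate |
|---|---|---|---|---|
| 0% | 0 | 0 | 9.2 | 40.5% |
| 5% | 0.53 | 0.415 | 9.7 | 42.4% |
| 10% | 1.06 | 0.664 | 10.2 | 44.3% |
| 20% | 2.11 | 0.895 | 11.5 | 48.5% |
| 30% | 3.17 | 0.970 | 13.1 | 53.1% |

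If 9.2 months is instead already a progression-only figure, the progression-or-death median is 9.2(1 − s): 8.7, 8.3, 7.4 and 6.4 months at 5%, 10%, 20% and 30%.

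**Small-sample behaviour (simulated trials of 17 responders).**
- Fixed 8-week scans, deaths censored at the last scan: the median is identical in 71.1% (s = 10%) or 48.5% (20%) of runs; it rises by at most one scan interval in 13.6% or 18.9%; it rises by more or becomes not reached in 15.3% or 32.6%. At s = 5% it is identical in about 85%.
- Exactly one such death (s = 10%): identical in 70.3%.
- Scan windows of ±1 week: identical in 65.9% or 42.2%.
- Median not reached, continuous times: 10.7% of runs under the progression-or-death rule, against 18.1% or 28.8%. Under 8-week scans: about 14%, against about 23% or 33%.

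**How large can s be?** Let the death hazard be sλ in response and μ after progression. Survival from response is exp(−λt) + (1 − s)λ[exp(−μt) − exp(−λt)] / (λ − μ), set to 0.5 at t = 29.7 − 2 = 27.7 months. Solving for μ, the ratio μ/(sλ) is 5.7, 2.4 and 1.2 at s = 10%, 20% and 30%, and reaches 1 at 33%. With response at 4 months it is 6.6, 2.8 and 1.4. A share of 30% requires death to be barely more likely after progression than in response, so it is close to a ceiling.

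**Scale and timing.** The approximate 95% CI is 9.2 × exp(±1.96/√10.56) = 5.0 to 16.8 months. At the first analysis, taken as 2 months after the last enrolment, follow-up from response is 0 to 6 months: P(event) = 1 − (1 − 0.6363)/0.4521 = 0.195, so 3.32 events and 0.33 to 0.66 such deaths at 10% to 20%. The issue therefore mainly concerns the later analysis ("the amended analyses on efficacy and safety will be conducted after the End of Study").

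**The case against.** The strongest reply is that this is a descriptive secondary endpoint with no target. No decision in the documents depends on it, and the bias is smaller than the sampling error. The share is assumed, and the provisions on scanning and follow-up may keep it low. At 5%, about half a death is expected and the likelier outcome is none. In the model above, a 20% share implies a median survival after progression of about 19 months, whereas the Study Rationale gives 3.2 months for PD/NR subjects; that is a different population, so it sets no strict bound, but it lends the larger shares no support. The event count assumes no dropout and early response. Time to objectively documented progression is a coherent endpoint in itself, since death is captured in PFS and OS. The consistency criterion with SADAL concerns ORR only, and if SADAL's DOR was progression-only, the present definition is the matching one. Finally, the text available is a synopsis and assessment schedule, so a censoring rule elsewhere cannot be excluded.

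Much of this stands as to size: the effect may be nil, and the 20% figures are not a central estimate. It does not remove the point. The plan neither presents a progression-only DOR as deliberate nor says what happens to deaths. A confidence interval displays sampling error but not a bias that runs one way. The SADAL argument favours reporting both versions, which the fix does.

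**Conclusion.** The concern holds. As written, DOR and PFS treat death differently, and DOR is biased upward relative to a progression-or-death DOR whenever a responder dies without centrally documented progression. If no such death occurs there is no bias. Under constant hazards, an assumed share of 5% to 20% lifts a 9.2-month median by 0.5 to 2.3 months on average, although in a single trial of 17 responders the estimated median often does not move. The share itself cannot be derived from the documents. The primary endpoint and its power are unaffected. It should be fixed because the remedy is cheap and the rule ought to be settled before the data are seen.

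**What to change.** Define DOR as the time from first centrally assessed CR or PR to the earlier of first centrally documented progression and death from any cause. Censor responders who are alive and progression-free at their last adequate disease assessment. State how deaths after missed assessments or after new anticancer therapy are handled (event at the death date, or censored at the last adequate assessment), because counting a late death as an event can itself lengthen DOR. Apply the same rule to PFS. Report the progression-only version as a sensitivity analysis, so that SADAL can be compared like for like whichever definition it used.

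The cost is one clause, a short censoring paragraph and one extra table. Survival status and later anticancer therapy are already collected (Table 1, footnote 28). The one drawback is that the reported DOR may be somewhat shorter.

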### **Discontinuation Criteria:**

A subject may be discontinued at the discretion of the Investigator for any of the following reasons, the investigator should make the decision after timely communication with the clinical trial monitor in specific cases.

- Disease progression, as assessed by the Investigator and confirmed by the central radiological review, defined according to the revised Lugano criteria for response assessment of lymphoma (Cheson, 2014)
  - For subjects with disease progression on imaging assessment, if disease progression is not clearly unequivocal and/or the patient is clearly deriving clinical benefit, after discussion with the Sponsor Medical Monitor, the Investigator may elect to continue the patient on study and repeat imaging within 4 to 8 weeks for confirmation or negation of PD.
- Disease progression as determined by the Investigator (should be radiographically confirmed whenever possible and must be comprehensively documented by the Investigator)
- Unacceptable adverse event(s) or failure to tolerate the study treatment
- Treatment delay of more than 28 days, except in specific cases approved by the Sponsor
- Any medically appropriate reason or significant protocol violation, in the opinion of the Investigator

The Investigator must remove a patient from study treatment for any of the following reasons:

- Patient decides to discontinue study treatment or withdraws consent
- Pregnancy

Subjects may decide to discontinue study treatment for any reason. Subjects who elect to discontinue study treatment will be asked to continue study participation so that follow-up information on disease progression and survival status may be obtained.

### **Statistical Summaries:**

The primary endpoint analyses will be conducted after at least one efficacy evaluation following the enrollment of the last patient to the study (including efficacy and safety), and the amended analyses on efficacy and safety will be conducted after the End of Study.

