### **Study Design**

This is an open-label, single arm, and registered study. About 60 subjects with relapsed or refractory DLBCL plan to be enrolled in about 10 study sites of the study. It is planned that at least 50% (~30 subjects) will have the GCB subtype of DLBCL. Enrolled subjects will be treated with a fixed dose, 60 mg of ATG-010, orally, twice weekly, each 4-week a cycle. Subjects should remain on the study treatment of ATG-010, until either PD or occurrence of unacceptable toxicity.

Confirmed evidence of DLBCL progressive or failed to the last treatment regimen is required for study entry, and subjects must have measurable disease at screening per the Lugano criteria for response assessment (Cheson, 2014).

Disease assessment (tumor measurement) will be made by PET-CT and Contrast-enhanced CT (Tumor measurement) at screening (within the first 14 days of Cycle 1 Day 1), enhanced CT should include the neck, chest, abdomen, pelvic cavity (including the inguinal/femoral region), if clinically indicated, as well as other anatomical sites. If CT is contraindicated, MRI scan will be performed. PET-CT and contrast-enhanced CT scans will be performed on Cycle 3 Day 1 ( $\pm$  1 week) and then every 8 $\pm$  weeks (ie, Day 1 of odd numbered cycles) until disease progression is confirmed by the central radiological review. The PET-CT is allowed at alternating assessment time points (ie, every 16 weeks, or every other scan) if PET-CT cannot be performed for every assessment. If CT scan suggests the possibility of obtaining CR, PET-CT should be performed for confirmation. Results of PET-CT and contrast-enhanced CT scans performed beyond a predetermined time point should be recorded on the eCRF and images of all disease assessment scans performed during the study period will be provided to the central radiological review.

Bone marrow aspirates and/or biopsies will be taken within 1 month prior to first dose (baseline) to assess bone marrow involvement. The bone marrow biopsy will be repeated whenever clinically indicated to confirm CR in only those subjects who had DLBCL with known bone marrow involvement prior to dosing.

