#### **Duration of Study:**

The enrollment period for the study is expected to be 6 months, the end of study will be defined as 12 months after the last patient enrolled in the study, has withdrawn consent, has died, or has been lost to follow-up, (whichever occurs first). In addition, Sponsor may at any time decide to discontinue the study for reasons including but not limited to security.

Upon completion of this study, Sponsor will provide continuous treatment (as determined by the investigator) to the subjects who still have clinical benefits. The study drug may be provided through additional extension studies or in other forms at the discretion of the Sponsor.

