### ***Determination of Sample Size***

This study is a bridging study based on an international multicenter clinical trial SADAL, and aims to verify the efficacy and safety of ATG-010 single drug in the treatment of relapsed or refractory DLBCL in the Chinese subjects. Consistent requirements of efficacy results and the SADAL study are that the point estimate of ORR in the bridging study falls within the 95% CI of the SADAL study (ORR of SADAL study: 28.3%; 95% CI: 20.7% - 37.0%). 60 subjects are

enrolled in SEARCH. If ORR reaches 28.3%, it can provide more than 90% power to make its assumed ORR to be above 20.7% and obtain sufficient safety data in Chinese subjects.

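### The primary ORR may be read after a single post-enrolment evaluation with no minimum follow-up per subject; a cut at that floor can only lower ORR, and the stated power has almost no reserve

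*Combined protocol and SAP*

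**What the plan says.** Under Statistical Summaries the first readout is set as follows: "The primary endpoint analyses will be conducted after at least one efficacy evaluation following the enrollment of the last patient to the study". The same sentence adds that "the amended analyses on efficacy and safety will be conducted after the End of Study". The wording gives a floor and no minimum number of weeks, cycles or scans per subject. No other section supplies one.

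The endpoint is "ORR by central radiological review: PR + CR", with no time point attached, so I read it as a response at any scan up to the cut. Efficacy Assessment puts every subject who took at least one dose in the denominator. Under Study Design and in Table 1, footnote 21, the first post-baseline scan is at Cycle 3 Day 1 (about week 8, with a one-week window). Later scans are every 8 weeks until centrally confirmed progression.

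Determination of Sample Size requires that "the point estimate of ORR in the bridging study falls within the 95% CI of the SADAL study", quoting "ORR of SADAL study: 28.3%; 95% CI: 20.7% - 37.0"%. The power statement is "If ORR reaches 28.3%, it can provide more than 90% power to make its assumed ORR to be above 20.7"%. On size and pace: "About 60 subjects with relapsed or refractory DLBCL plan to be enrolled in about 10 study sites", and "The enrollment period for the study is expected to be 6 months". End of study is nominally 12 months after the last enrolment.

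**The concern.** With a 6-month enrolment period and a scan every 8 weeks, a cut about 8 weeks after the last enrolment leaves the latest enrollees with one opportunity to be scored as responders. Anyone among them who would first respond at week 16 or later is counted as a non-responder. More scans can raise a subject's best response but cannot lower it, and nobody leaves the denominator, so the direction of any error is fixed: downward.

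The rule uses the point estimate with no margin, so one responder can change the conclusion: 12/60 = 20.0% is outside the range and 13/60 = 21.7% is inside. The power statement makes no allowance for incomplete follow-up. At stake is a result declared inconsistent with SADAL because of when the data were cut, not because of how the drug performed.

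**Working it through.** **Inputs from the documents.** n = 60; benchmark ORR 28.3% with limits 20.7% and 37.0% (Determination of Sample Size); scans at weeks 8, 16, 24 and so on (Table 1, footnote 21); enrolment 6 months, about 26 weeks (Duration of Study).

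**Assumptions.** Even accrual over the 26 weeks. The share *f* of eventual responders who first respond after scan 1 is not in the documents, so a range is shown. The single evaluation is taken to be the last patient's own week-8 scan.

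**1. Decision limits.** 0.207 × 60 = 12.42, so at least 13 responders are needed. 0.370 × 60 = 22.2, so at most 22 are allowed.

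**2. The plan's own figure.** With X ~ Binomial(60, 0.283), P(X ≥ 13) = 0.903. The stated power is reproduced, for the lower limit only and with complete follow-up. The full two-sided rule has P(13 ≤ X ≤ 22) = 0.844.

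**3. Reserve.** P(X ≥ 13) drops below 0.90 once the effective ORR falls below 28.19%, only about 0.1 percentage points under the assumed 28.3%.

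**4. Subjects with one scan at the floor.** 60 × 8/26 = 18.5, taken as 18; the other 42 are treated as complete.

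**5. Effect of the cut.** X is the sum of Binomial(42, 0.283) and Binomial(18, 0.283 × (1 − f)). Expected ORR = 0.283 × (1 − 0.3f), because 18/60 = 0.3.

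| f | Expected ORR | P(X ≥ 13) | P(13 ≤ X ≤ 22) |
|---|---|---|---|
| 0 | 28.3% | 90.3% | 84.4% |
| 2% | 28.1% | 89.8% | 84.2% |
| 5% | 27.9% | 89.1% | 83.9% |
| 10% | 27.5% | 87.7% | 83.3% |
| 20% | 26.6% | 84.5% | 81.4% |
| 30% | 25.8% | 80.8% | 78.6% |

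Break-even with the stated 90%: (1 − 0.2819/0.283)/0.3 gives f of about 1.3%.

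**6. Subjects with two or three scans also incomplete, and the effect of waiting for a second scan.** Even accrual gives about 18, 18, 18 and 6 subjects with one, two, three and four or more scans at the floor. Waiting 8 more weeks gives every subject one more scan. Each group's response probability is 0.283 times the assumed cumulative share of responders already in response by its latest scan (100% from the fourth scan on).

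| Assumed share by scans 1/2/3 | P(X ≥ 13), one-scan cut | P(X ≥ 13), two-scan cut |
|---|---|---|
| 90/97/99% | about 86% | about 89% |
| 80/93/98% | about 81% | about 88% |
| 70/90/97% | about 75% | about 87% |

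The second scan recovers roughly three quarters of the loss from 90.3% (3 of 4, 7 of 9 and 12 of 15 points).

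**The case against.** **The size is assumed.** This stands. The documents give neither time to response nor an accrual curve. If nearly all responses appear by week 8, the loss is negligible. A reader might infer that the rule as written does bias ORR and does cost power. That needs both late first responses and a readout at the floor, and the wording permits a later cut.

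**The two-sided rule loses less.** This also stands. An early cut reduces overshoot above 37.0% as well, so the 13-to-22 probability falls by only 1.1, 3.0 and 5.8 points at f = 10%, 20% and 30%.

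**The error is conservative.** Correct. An early cut cannot inflate ORR, so a false claim of efficacy does not follow. The exposure is a false finding of inconsistency.

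**SADAL maturity.** A reader might infer that the benchmark rests on much longer follow-up, because the Study Rationale mentions 23 months. That figure is a median duration of response among complete responders, from the data cut with ORR 29.6% in 115 subjects. It is not a follow-up time, it does not belong to the 28.3% figure, and it says nothing about when responses first appeared. The follow-up behind 28.3% is not stated.

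**Two readouts.** A reader might infer that the deciding analysis is undefined. The first readout is already labelled primary and the later one amended, so the natural reading is that the first decides. The sample-size section does not say so, which calls for clarification only. A move from 12/60 to 13/60 between readouts is possible, but the documents support no probability for it.

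**Conclusion.** The point holds as a conditional weakness in the timing rule. The text, the missing minimum follow-up and the direction of the error are certain; the size is not. At the earliest permitted cut, with even accrual, the probability of exceeding 20.7% goes from 90.3% to between 89.8% and 80.8% as the late-responder share goes from 2% to 30%. It falls further, to about 75% to 86%, if subjects with two or three scans are also treated as incomplete under the shares assumed above. Because the reserve is so thin, a late share of only about 1.3% is enough to take the figure below the plan's own claim. This is a cheap improvement to the plan; the documents do not show that the planned analysis will be biased.

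**What to change.** In Statistical Summaries, set the primary cut-off at the date when every treated subject has had at least two scheduled post-baseline scans (through Cycle 5 Day 1), or has earlier progressed, died or withdrawn. State there and in Determination of Sample Size that this cut decides consistency with SADAL, and that the End of Study ORR is an update.

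The cost is a readout about 8 weeks later than the earliest now permitted. No subjects or scans are added, because follow-up to 12 months after last enrolment is already planned. Two scans restore most of the stated power but not all of it. If the sponsor wants to stay closer to 90%, a third scan costs another 8 weeks: under the 80/93/98% assumption, 18 subjects would then be 2% short and the rest complete, which is the 89.8% row of the first table. Whichever is chosen, the power statement should say what follow-up it assumes.
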